2. BACKGROUND AND RATIONALE

Prostate cancer (PCa) is the most frequently diagnosed non-cutaneous cancer in male patients worldwide (1). While many cases are indolent and progress slowly, PCa remains a significant cause of morbidity and mortality in Europe, with over 110,000 deaths recorded in 2020 (2). In its localised stage, clinically significant PCa can be treated with curative intent using local therapies such as radical prostatectomy (RP), radical radiotherapy (RT), brachytherapy or focal ablative treatments (3). RP is the most common surgical treatment, with approximately 8,000 robot-assisted radical prostatectomies (RARP) performed in the UK each year. However, RP is associated with important side effects, most notably erectile dysfunction and urinary incontinence, which can be associated with decreased quality of life (4).

To decrease the incidence of these side effects, surgical refinements such as nerve-sparing (NS), bladder neck sparing, dorsal venous complex “hood-sparing” and Retzius-sparing techniques have been developed (5). These approaches improve preservation of tissues around the prostate and are associated with better functional outcomes (6). However, they require dissection closer to the prostatic capsule, which increases the risk of positive surgical margins (PSM) (7). The risk is particularly high when the tumour extends beyond the prostate (extra-prostatic extension, EPE) in

the posterolateral areas of the prostate (8). In such cases, attempting nerve preservation may increase the risk PSM, which could only be detected once the final histopathology formalin-fixed paraffin-embedded analysis (FFPE) results are reported.

Retrospective studies suggest that small, unifocal, low-grade PSMs on FFPE are not associated with cancer recurrence. In contrast, larger, multifocal or high-grade PSMs significantly increase recurrence risk and often necessitate salvage treatments, which carry their own side effects (9). Therefore, careful pre-operative planning is essential to identify men who can safely undergo tissue-sparing RARP without compromising oncological outcomes. Current decision-making relies on combining clinical features, prostate biopsy histology and mpMRI in nomograms or independently (10). However, predictive nomograms have poor external validity (11, 12), and mpMRI has limited accuracy in detecting EPE (13, 14). As a result, many men are denied nerve-sparing surgery when it could have been performed safely.

To address this limitation, the Martini-Klinik in Germany developed the NeuroSAFE technique, which involves intraoperative frozen section (FS) analysis of the posterolateral prostate margins (15). We recently completed a phase III randomised controlled trial demonstrating that NeuroSAFE improves post-operative erectile function and early urinary continence (17). The rate of bilateral nerve-sparing was significantly higher in the NeuroSAFE arm (82.1%) compared with controls (56.4%), facilitated by pre-specified criteria that allowed small, unifocal or low-grade PSMs to be left in place without secondary resection. Patients in the NeuroSAFE arm who would not otherwise have received nerve-sparing surgery derived the greatest benefit in terms of erectile function recovery.

Despite its efficacy, NeuroSAFE is labour- and resource-intensive. It requires at least two dedicated histopathology technicians and a uropathologist, and takes a median of 68 minutes to perform while the patient remains under general anaesthesia. Although this did not result in patient harm, it poses a substantial burden on pathology and urology services, limiting widespread adoption (18).

Fluorescence confocal microscopy (FCM) is an emerging imaging technique that uses fluorescent dyes to generate high-resolution cellular-level images of fresh tissue (19). FCM can reliably differentiate between tissue types and has demonstrated strong diagnostic performance in detecting cancer (20). Compared with FS, FCM requires less time, expertise and consumables, making it more feasible for routine use. FCM is already established in dermatological oncology (21) and has shown promise for diagnosing PCa in core biopsies (22). A systematic review, including five studies assessing 148 prostate specimens, reported aggregated sensitivity and specificity above 85% (23). In a prospective study, Baas et al. found a concordance rate of 0.8 between FCM and NeuroSAFE (24).

These studies required slicing the prostate margins before sampling, which required the presence of pathologist to perform and complicated subsequent pathological assessment. To overcome this, we developed LaserSAFE, a standardised technique for assessing intact specimens using FCM (25). In a pilot study, LaserSAFE demonstrated encouraging sensitivity across both expert and novice readers blinded to final histopathology results (26). More recently, we completed a feasibility study comparing LaserSAFE and NeuroSAFE, showing 91% sensitivity for detecting margins greater than 0.5 mm. However, we could not expand the feasibility study to other sites due to challenges associated with adopting NeuroSAFE in other National Health Service (NHS) centres.

The available evidence supports LaserSAFE as a promising alternative to NeuroSAFE, sharing the same underlying goal of enabling safe nerve-sparing in patients who might otherwise not receive it. The NeuroSAFE PROOF study has already demonstrated, with level 1 evidence, that this approach

can lead to improved patient outcomes (17). However, as previously reported and confirmed in our feasibility study, implementing NeuroSAFE in the NHS is not currently feasible due to the resource and time demands required.

Several important knowledge gaps must be addressed before LaserSAFE can be safely introduced into clinical practice. Unlike standard FFPE analysis, LaserSAFE evaluates tissue en face rather than in cross-section (19). This change in orientation presents a challenge for pathologists, who must adapt to interpreting margins from a new perspective. Therefore, the most critical parameter to assess is the sensitivity of the technique, as false-negative results, or failing to detect a PSM, could expose patients to adverse oncological outcomes.

An important caveat is, that evidence suggests that the length of a PSM correlates with the risk of recurrence, with margins smaller than 2 mm not associated with increased recurrence risk (27). Consequently, the NeuroSAFE protocol recommends secondary resection only when the PSM exceeds 2 mm, representing a clinically significant margin. However, margins assessed en face appear larger than those evaluated in cross-section, due to differences in orientation and tissue shrinkage during frozen or paraffin processing. Resecting small, non-significant margins could therefore compromise functional outcomes without providing oncological benefit.

At present, there is no established threshold for what constitutes a clinically significant positive margin in en-face analysis that would justify secondary resection. This study protocol adaptive design will answer this critical gap in knowledge. Addressing these questions will be crucial to ensure the safe adoption of LaserSAFE. If validated, this technique could enable many more centres to provide real-time margin analysis, broadening access to nerve-sparing surgery and potentially improving patients' quality of life. We have conducted several patient and public events during the conduct of the NeuroSAFE PROOF study where participants have expressed support for the exploration of new technologies that could expand access to real time analysis of surgical margins.

We therefore propose the first prospective study to assess the clinical performance of LaserSAFE in guiding nerve-sparing decisions for men undergoing RARP for localised PCa. The study aims to define its accuracy metrics and establish the optimal margin length threshold to maximise nerve preservation without compromising oncological safety.

3. OBJECTIVES AND OUTCOME MEASURES/ENDPOINTS

Objectives are set in the context of patients diagnosed with localised prostate cancer scheduled for robot-assisted RP with a relative contraindication on surgical to perform intrafascial nerve sparing on at least 1 side of the prostate, who have not had previous PCa treatment.

3.1. Primary Objective

- To establish the sensitivity of pathology led LaserSAFE image interpretation to guide nerve-sparing decisions during radical prostatectomy

3.2. Secondary Objective(s)

- To evaluate the accuracy metrics of pathology led LaserSAFE image interpretation against FFPE
- To establish the optimal cut-off criteria to suggest a secondary resection should be performed based on LaserSAFE results
- To describe the prevalence of PSM in the cohort
- To evaluate the rate of PCa recurrence within 12 months of surgery
- To evaluate the urinary incontinence and erectile function scores of patients at 3 and 12 months after surgery using the EPIC-26 questionnaire

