3.3. Outcome Measures/Endpoints

- Primary endpoint
 - Sensitivity of LaserSAFE to detect positive margins in the posterolateral area of the prostate of more than 3 mm
 - Sensitivity will be monitored across the trial when the first 150, 300 and 500 participants have been recruited.
 - If sensitivity decreases below 85%, trial methodology will be reviewed and if considered appropriate the trial will be stopped.
- Secondary endpoints
 - Define the cut-off point for triggering secondary resection based on the prevalence of residual prostate cancer in secondary resections.
 - Overall sensitivity, specificity, PPV and NPV of LaserSAFE compared to FFPE analysis for any length of PSM
 - Overall specificity, PPV and NPV of LaserSAFE compared to FFPE analysis for any PSM > 3 mm.
 - Rate of residual prostate cancer in secondary resections of the neurovascular bundle
 - Prevalence of PSM detected by paraffin analysis in the overall cohort.
 - Prevalence of PCa biochemical recurrence or salvage treatment within 12 months after surgery
 - Mean score for EPIC-26 urinary incontinence domain at baseline, 3 and 12 months after surgery
 - Mean score for EPIC-26 erectile function domain at baseline, 3 and 12 months after surgery

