6.3.1.2. Lasersafe Technique

The LaserSAFE procedure is performed using an FCM called the Histolog[®] scanner developed by Samantree[®] which can be placed within the operating room. Histolog Scanner, Histolog Viewer, and accessories will be used according to the Instructions for Use. No modification to the CE-Mark/UKCA-Mark/FDA 510k clearance approved intended use will be made. The Histolog[®] scanner produces digital images with high, micrometre-range resolution and enables the visualization of tissue microstructures down to the cellular level. The microscope can image an area of 48x36 mm in approximately 60 seconds. Its operating principle is based on non-ionizing, low-power optical radiation (Laser) with a wavelength of 488±5 nm, and it uses a point illumination conjugated with a pinhole in front of the detector to eliminate out-of-focus signals.

The protocol of image acquisition is as follows: the prostate is cleaned using damp gauze and completely submerged in a solution that contains a photoreactive agent Histolog Dip[®] for 10 seconds. The specimen is rinsed with 0.9% NaCl solution, placed on the Histolog[®] scanner and lightly compressed using a mouldable weight. An initial live view scan confirms adequate positioning and stability of the specimen to avoid movement artefacts. If the preliminary scan is deemed satisfactory, a high-resolution digital image is acquired and stored in the microscope hard drive. The prostate is rotated to image the contralateral side. Once both posterolateral surfaces are imaged the prostate is placed in a container and fixed with formalin. Image acquisition takes less than 5 minutes. A pathologist will interpret the images on site or remotely depending on site specific requirements and complete a reporting case report form. The findings will be communicated directly to the surgeon.

Nerve sparing decisions will be guided by the result of the LaserSAFE technique.

The presence of cancer cells at the surface margin of the specimen will constitute a positive margin. Detailed results including the length of positive margin in 2 dimensions and multifocality, will be collected and included in the results.

In the presence of a posterolateral PSM, the performance of secondary resection (SR) of the ipsilateral neurovascular bundle (NVB) will be made if any of the following are present:

- (1) Multiple areas of PSM where the sum of each maximum dimension is >3 mm
- (2) any single PSM area >3 mm in maximum dimension

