9.2. Secondary Outcomes

- Evaluate the accuracy metrics of LaserSAFE image interpretation against FFPE.
 - The following items will be calculated and reported:
 - Sensitivity, specificity, PPV and NPV of LaserSAFE compared to FFPE analysis for any length of PSM
 - Specificity, PPV and NPV of LaserSAFE compared to FFPE analysis for PSM > 3 mm.
- Determination of Margin Length Cut-off for Secondary Resection

The study will evaluate the optimal cut-off for positive margin length that should trigger a secondary resection, with the aim of maximising nerve-sparing without compromising oncological safety.

- Decision Rules:
 - Interim analyses will be performed after recruitment of 150, 300, and 500 participants.
 - At each interim analysis, the prevalence of residual tumour in secondary resections will be calculated across margin length thresholds in 1 mm increments.
 - If the prevalence of residual tumour at a given threshold is <15%, the cut-off for secondary resection in the next cohort will be increased in 1 mm increments, up to a maximum cut-off of 6 mm.
 - If the prevalence of residual tumour is ≥15% at any threshold, that cut-off will be retained and applied to all subsequent cohorts for the remainder of the study.
 - No further upward adjustment will be made once the 6 mm maximum cut-off is reached.

This adaptive design ensures that the margin length threshold used to guide secondary resection is based on prospective evidence, optimising oncological safety while maximising opportunities for nerve-sparing.

- Descriptive outcomes:
 - Rate of residual prostate cancer in secondary resections of the neurovascular bundle

- Prevalence of PSM detected by paraffin analysis in the overall cohort.
- Prevalence of PCa biochemical recurrence or salvage treatment within 12 months after surgery
- Mean score for EPIC-26 urinary incontinence domain at baseline, 3 and 12 months after surgery
- Mean score for EPIC-26 erectile function domain at baseline, 3 and 12 months after surgery

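### The adaptive rule can only hold or raise the secondary-resection cut-off between 3 and 6 mm, so it cannot show that 3 mm is optimal, and 6 mm is only the permitted maximum unless data above it say more

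*Protocol*

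**What the plan says.** The claim appears in several places. Section 3.2 gives the objective as "To establish the optimal cut-off criteria to suggest a secondary resection should be performed based on LaserSAFE results", and the study summary repeats it. The last paragraph of section 2 says the study will "establish the optimal margin length threshold to maximise nerve preservation without compromising oncological safety". Section 9.2 again speaks of the optimal cut-off, and section 1.1 of the best threshold. The endpoint in 3.3 is worded more neutrally but fixes the evidence to be used: "Define the cut-off point for triggering secondary resection based on the prevalence of residual prostate cancer in secondary resections".

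The starting trigger is in 6.3.1.2. Secondary resection follows "any single PSM area >3 mm in maximum dimension" or "Multiple areas of PSM where the sum of each maximum dimension is >3 mm". Section 11.5 lists departure from these criteria as an example of a protocol violation.

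The rule is in 9.2:
- Timing: "Interim analyses will be performed after recruitment of 150, 300, and 500 participants".
- Below 15% residual tumour, the cut-off for the next cohort goes up in 1 mm increments, to at most 6 mm.
- Otherwise: "If the prevalence of residual tumour is ≥15% at any threshold, that cut-off will be retained and applied to all subsequent cohorts".
- At the top: "No further upward adjustment will be made once the 6 mm maximum cut-off is reached".

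No step lowers the cut-off. Section 2 also states that no en-face threshold has yet been established.

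**The concern.** An optimum is a claim about both sides: a lower value would be worse, and so would a higher one. This rule looks in one direction only, from a start that section 2 does not present as an established en-face threshold. If it stops at its first position, the trial has learnt that the cut-off should not be raised. It has not learnt whether a lower cut-off would have met the same 15% criterion.

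What is at stake is the conclusion other centres would take away. Under the objective as worded, a retained 3 mm could be adopted as an evidence-based optimum when it is the starting assumption carried through. The primary endpoint, the sample size and the conduct of surgery are not affected.

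**Working it through.** The protocol gives no computed figure for the cut-off objective. Its only calculation is for sensitivity, and it reproduces: 1.96² × 0.91 × 0.09 / 0.05² = 125.85, so 126; 126 / 0.20 = 630; 630 × 1.10 = 693. The cut-off question does not depend on it.

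**1. Possible results.** Inputs: start 3 mm (6.3.1.2); looks at 150, 300 and 500 participants, up if below 15%, lock if 15% or more, cap 6 mm (9.2). With one 1 mm step per look there are 2³ = 8 patterns of outcomes:

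| Outcome at the looks | Patterns | Final cut-off |
|---|---|---|
| 15% or more at the first | 4 | 3 mm |
| below, then 15% or more | 2 | 4 mm |
| below, below, then 15% or more | 1 | 5 mm |
| below at all three | 1 | 6 mm |

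These are counts of patterns, not probabilities. If several steps per look are allowed, the set is still 3, 4, 5 and 6 mm. No path ends below 3 or above 6.

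**2. Lower end.** Residual tumour is known only where tissue is secondarily resected. A single or summed length of 3 mm or less does not trigger resection, so the planned number of resections in that range is 0 among all 693 participants. Observed prevalences of 15%, 40% and 80% just above 3 mm all lead to the same action: retain 3 mm.

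**3. Upper end.** A margin longer than 6 mm exceeds every permitted cut-off, so it is resected throughout the trial and its residual prevalence is observed. Only the decision is capped. With one step per look, 6 mm is first reached at the 500 look. The remaining 693 − 500 = 193 participants are then treated under it, and no later look re-examines the cut-off. The data above 6 mm can still be read at the final analysis.

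**4. Could a result at the limits arise?** This is an illustration only; its assumptions are not in the protocol. They are: 0.20 × 0.91 = 18.2% of participants with a detected margin above 3 mm (150 × 0.182 = 27.3 resections by the first look); lengths of 3 mm plus an exponential with mean 3 mm; residual risk rising on a logistic scale by 0.5 per mm; 3,000 runs; one step per look. The table shows the final cut-off by the length at which true residual risk crosses 15%.

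| True crossing | 15% rule read on the 1 mm bin above the cut-off | 15% rule read on all resections above the cut-off |
|---|---|---|
| 1 mm | 3 mm in 89% | 3 mm in about 100% |
| 2 mm | 3 mm in 74%, 4 mm in 24%, 5 mm in 2% | 3 mm in about 100% |
| 8 mm | 6 mm in 87% | 6 mm in 16% |
| 10 mm | 6 mm in 97% | 6 mm in 74% |

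Endings at the limits are plausible. On the bin reading, a true crossing below the start also yields 4 or 5 mm in about a quarter of runs (24% + 2%), so an interior result does not by itself locate the threshold.

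**The case against.** The range is pre-specified in plain view, and the direction follows from the stated aim of preserving nerves without losing oncological safety. The 6 mm maximum can be read as a deliberate safety limit. The start is also reasoned: section 2 says cross-sectional margins under 2 mm are not associated with more recurrence, that en-face margins look larger, and that resecting insignificant margins may cost function for no benefit. All of this stands, and the point does not challenge the range or the surgical rule. Section 2 gives no conversion from cross-section to en-face length, however. A reader who infers from the 2 mm figure that the right en-face value lies below 3 mm goes beyond the document.

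A reader might also infer that both ends are equally blind, so that 6 mm could never be more than a limit of the search. The protocol does not support that. Data above 6 mm are collected, and if residual prevalence there is 15% or more, 6 mm has support.

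Nor does any section say that a final 3 mm or 6 mm will be reported as optimal without qualification. That is an inference from the objective's wording, and a statistical analysis plan could add a reporting rule. What remains is that the objective and the decision rule are both fixed in this protocol and differ in scope.

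Finally, residual prevalence by increment would tell 15% from 80%, and biochemical recurrence or salvage treatment is recorded to 12 months. This is indirect evidence about 3 mm, so it would be wrong to say the data are silent. But the recurrence outcome is descriptive only and does not enter the rule.

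**Conclusion.** The point holds, chiefly at the lower end. The design returns one of four values (3, 4, 5 or 6 mm), moves only upward, and yields no residual-tumour data at or below 3 mm. A final 3 mm means no support for raising the cut-off; it cannot be called optimal. A final 6 mm is the limit of the permitted adjustment unless the observed prevalence above 6 mm supports it.

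This rests on the text of 6.3.1.2 and 9.2 and on the resection criteria being followed. It does not rest on the illustrative simulation. It is a fault in what the objective claims. It does not show that any of the lengths is wrong.

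**What to change.** Restate the objective in the study summary, 3.2 and 9.2, and align the wording in 1.1 and section 2. Suggested text: to determine whether the LaserSAFE length that triggers secondary resection can be raised above the 3 mm start, within the pre-specified range of 3 to 6 mm, under the protocol's 15% residual-tumour rule.

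Add a short reporting rule:
- Final 3 mm: no support for raising the cut-off; shorter lengths not tested.
- Final 6 mm: the maximum permitted by the design, reported with the observed residual prevalence above 6 mm and its 95% confidence interval.
- Any final cut-off: residual prevalence with 95% confidence interval by 1 mm increment. A result of 4 or 5 mm should not be labelled as a threshold located by the trial.

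The surgical rule, the looks and the sample size stay as they are. The cost is a few sentences and a more modest headline claim.

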3.3. Outcome Measures/Endpoints

- Primary endpoint
 - Sensitivity of LaserSAFE to detect positive margins in the posterolateral area of the prostate of more than 3 mm
 - Sensitivity will be monitored across the trial when the first 150, 300 and 500 participants have been recruited.
 - If sensitivity decreases below 85%, trial methodology will be reviewed and if considered appropriate the trial will be stopped.
- Secondary endpoints
 - Define the cut-off point for triggering secondary resection based on the prevalence of residual prostate cancer in secondary resections.
 - Overall sensitivity, specificity, PPV and NPV of LaserSAFE compared to FFPE analysis for any length of PSM
 - Overall specificity, PPV and NPV of LaserSAFE compared to FFPE analysis for any PSM > 3 mm.
 - Rate of residual prostate cancer in secondary resections of the neurovascular bundle
 - Prevalence of PSM detected by paraffin analysis in the overall cohort.
 - Prevalence of PCa biochemical recurrence or salvage treatment within 12 months after surgery
 - Mean score for EPIC-26 urinary incontinence domain at baseline, 3 and 12 months after surgery
 - Mean score for EPIC-26 erectile function domain at baseline, 3 and 12 months after surgery

